1.0 Purpose of the Study

The proposed study is the second phase of a project assessing the feasibility and effectiveness of enhancing the early detection of melanomas among women, who are engaging in health promotion by having mammograms. The initial phase of the project framed risk messages, developed posters and brochures with the input provided by women undergoing screening mammograms, and assessed the feasibility of delivering the program during the mammogram visit at the Lynn Sage Comprehensive Breast Center of Northwestern Medicine/ Prentice Women's Hospital. Now, we seek to evaluate performance of skin self-examination (SSE) by women, who receive information during their mammogram appointment, and follow-up with dermatology for a melanoma screening examination.

In the second phase, a more intensive intervention in which women will not only receive information about SSE, but will also receive a reminder to perform SSE one week after the screening mammogram and information on how to schedule an appointment with dermatology will be provided. The number of women who perform SSE at home and find a concerning mole (lesion), number who see a dermatologist, and number who have a concerning lesion biopsied will be compared in two arms of the study 1) women who receive the intensive intervention 2) women who receive the informational brochure about SSE alone.

Our hypothesis is that women who receive more the intensive educational intervention will be more likely to perform SSE at home and schedule a follow-up dermatologist appointment as compared to those who receive the information brochure alone. This project builds upon [name]'s successful SSE training program for melanoma patients that resulted in patients' accurate evaluations of suspicious lesions relative to dermatologists' skin examinations.⁴

The study aims are as follows:

1. Assess whether SSE education introduced during routine screening mammography encourages women to implement SSE at home, find concerning lesions, and seek follow-up with a dermatologist.
2. Assess the effectiveness of additional reminders to perform SSE and providing information on how to schedule follow-up with a dermatologist on participant performance of SSE with identification of a concerning lesion or scheduling a screening examination with a dermatologist without performing SSE.

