3.0 Procedures Involved

3.1 Study Design

Phase 1: *Delivery of educational SSE program.*

Each of the eight changing rooms of the Lynn Sage Comprehensive Breast of Northwestern Memorial Hospital will be equipped with a poster, brochures (Fig 1 and Fig 2) and cards with information about obtaining an appointment with a dermatologist for concerning skin lesions.

A woman research assistant will obtain consent to participate in the research and review of medical information, collect contact information and if the woman owns an iPhone X, 8+ or 8, and ensure receipt of an informational brochure. Women will be asked if they own an iPhone X, 8+ or 8 to assess the prevalence of these specific phones in the population of interest. These iPhones models are of particular interest to the research team as they offer superior image quality compared to older models. If a woman has this type of phone, she will be asked about her experience using it to take close-up pictures. The woman will be asked her preference for being contacted by email, telephone, or text message. The two arms of the study will be delivered on different weeks. During weeks 1,3,5 and 7 of the study period 400 women will be given brochures and a card with information on scheduling dermatology follow-up prior to check-out (Group 1), (Fig 3). During weeks 2, 4, 6 and 8 of the study period, 400 women will be given brochures to perform SSE at home and proceed to check-out of the mammogram area (Group 2). The women in Group 1 will also receive a reminder about performing a SSE one week after their mammogram visit via phone call,

Effect of SSE education delivered during the mammography experience.

email or text message. One month after the mammogram visit both groups will be called and surveyed to see if they checked their skin and/or made an appointment to see a dermatologist. Three months after the mammogram, both groups will be asked to participate in a complete survey (either via REDCap or telephone), including whether the women followed up in dermatology and if any concerning lesions were biopsied.

Fig 1. SSE Poster

[figure not shown]
[figure not shown]

Fig 2. Cover of SSE

[figure not shown]

Phase 2: Assessment of SEE Implementation

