A research assistant will be present at the mammography center to collect consent, telephone numbers, iPhone model information, and email addresses to have women sign onto REDCap to complete a survey. A telephone survey will be administered to each woman enrolled in the study in both groups (N=800) one month after the mammogram asking if she performed a SSE at home and whether a follow-up with dermatology was made. An anonymous REDCap survey may be used in place of the telephone call, depending on participant's preferred method of contact preference. Then, three months after the screening mammogram, an anonymous <2 minute REDCap survey will be sent via email to each woman enrolled in both groups to ascertain the number of women who identified that they were at increased risk for melanoma (history of sunburn, history of indoor tanning >10+sessions, family or personal history of skin cancer), performed a SSE at home, found a concerning lesion, made a follow-up appointment with a dermatologist, and had any concerning lesions biopsied. If participants do not complete the REDCap survey in 2 weeks, they will be called and surveyed via telephone. We anticipate a 20% attrition rate (Fig 3). Participants will be offered a \$10 Amazon gift card in appreciation of completing the one month survey and an additional \$10 for completing of a second REDCap survey three months after the mammogram visit.

Effect of SSE education delivered during the mammography experience.

Fig 3. CONSORT diagram for two arms of study

Effect of SSE education delivered during the mammography experience.

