3.2 Informed Consent, Participant Surveys, and Educational Intervention

As patients wait to have the mammogram, they will be screened for eligibility. Following completion of the mammogram, patients will return to the changing room and put on their clothing. After exiting the changing room in the Lynn Sage Comprehensive Breast Center of Northwestern Medicine/Prentice Women's Hospital and as they are preparing to leave, a research assistant (RA) will interview potential participants to acquire a randomly selected convenience sample of eligible participants (n=800). Participants will be invited to complete a survey that will assess knowledge of melanoma and the risk of developing a melanoma. They will be provided with a consent form and the research study will be discussed, questions will be invited and then they will be asked to sign a consent form and to fill out a registration form containing contact information. (see attached)

The complete survey includes general demographic items such as age, education, household income, race and ethnicity. The survey questions are as follows:

1. During your visit for mammography, did you notice any information about checking your skin for melanoma?

Yes No

2. Did you think this applied to you?

Yes No

3. If no, why not? (open ended)

4. If yes, why? (open ended)

5. Did you check your skin? (If no, please proceed to question #7)

Yes No

6. If yes, did you notice any concerning moles?

Yes No

7. If no, will you consider checking your skin in the future?

Yes No

8. If you found any concerning moles, did you make an appointment to see a dermatologist?

Yes No

The RA will record the responses.

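### Scheduling a dermatology appointment is part of the hypothesis, but the printed surveys never ask a woman with a clean SSE whether she made one, and no planned test covers it

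*Combined protocol and SAP*

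**What the plan says.** Section 1.0 states the hypothesis that women in the intensive arm will be "more likely to perform SSE at home and schedule a follow-up dermatologist appointment". The wording is not limited to women who find a lesion. Aim 2 is narrower. It concerns "participant performance of SSE with identification of a concerning lesion or scheduling a screening examination with a dermatologist without performing SSE". The same section lists the outcomes to be compared, among them the "number who see a dermatologist, and number who have a concerning lesion biopsied will be compared in two arms of the study". Scheduling is not in that list.

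Section 3.1 (Study Design) describes the data collection without condition. At one month "both groups will be called and surveyed to see if they checked their skin and/or made an appointment to see a dermatologist". The Phase 2 text repeats this for all 800 women: the telephone survey is described as "asking if she performed a SSE at home and whether a follow-up with dermatology was made". The three-month survey is to count women who, among other things, "made a follow-up appointment with a dermatologist, and had any concerning lesions biopsied".

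The items are printed in section 3.3. One-month item 5 has the same wording as item 8 of the section 3.2 survey: "If you found any concerning moles, did you make an appointment to see a dermatologist". At three months, item 7 asks about booking if a mole was found, item 8 asks if no SSE was done, and item 9 asks every woman whether she has had a dermatology appointment yet. The EMR review paragraph treats a yes to item 9 as showing that an appointment was made, and opens the record only then. Section 3.3 assigns the one-month call to Group 1 alone.

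The planned between-group tests are SSE performance and having seen a dermatologist (section 3.4), and SSE performance, biopsy, diagnoses and anxiety (section 14.0).

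**The concern.** Scheduling is one of the two behaviours named in the hypothesis, and the card handed to Group 1 before check-out is about scheduling. If booking is asked only in some branches of the questionnaire, the trial cannot count it for every woman, and a booking that nobody asked about cannot be recovered later. The EMR does not help, because it is opened only for women who report a visit. The reminder is meant to raise SSE, so the share of women in the unasked branch can differ between arms. Separately, no analysis is planned for scheduling, so that part of the hypothesis would go untested even with complete data.

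**Working it through.** **Skip pattern.** A woman falls into one of three branches. The table shows where a printed item asks her whether she made an appointment.

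| Branch | 1 month (item 5) | 3 months (items 7 and 8) | Item 9 (visit held) |
|---|---|---|---|
| SSE, concerning mole found | asked | asked (item 7) | asked |
| No SSE | not asked | asked (item 8) | asked |
| SSE, nothing found (clean SSE) | not asked | not asked | asked |

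Booking is therefore asked in 1 of 3 branches at one month and 2 of 3 at three months. For the clean-SSE branch, a no to item 9 mixes women who never booked with women whose visit is still to come. Item 9 also gives no start date, so a yes need not refer to the time since the mammogram.

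**Size.** The documents give 400 women per arm and 20% attrition, so 400 × 0.80 = 320 per arm. They give no SSE, mole-finding or booking rates, so there is no figure of the plan's own to reproduce. Every rate below is an assumption.

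Let s be the SSE rate, f the share of SSE performers who find a concerning mole, c the booking rate after a clean SSE, and v the share of those bookings attended by three months. Then

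bookings missed, as a share of all women = s × (1 − f) × c × (1 − v).

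With s = 50% v 30% (Group 1 v Group 2) and f = 15%:

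| c (Group 1 v 2) | v (Group 1 v 2) | Missed, Group 1 | Missed, Group 2 | Difference (points) |
|---|---|---|---|---|
| 0, or any c with v = 100% | – | 0 | 0 | 0 |
| 5% v 5% | 50% v 50% | 1.06% | 0.64% | 0.4 |
| 10% v 10% | 50% v 50% | 2.13% | 1.28% | 0.85 |
| 20% v 20% | 50% v 50% | 4.25% | 2.55% | 1.7 |
| 30% v 20% | 50% v 50% | 6.38% | 2.55% | 3.8 |
| 30% v 20% | 75% v 25% | 3.19% | 3.83% | −0.6 |

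For example, row five in Group 1 is 0.5 × 0.85 × 0.30 × 0.5 = 6.375%, or 20.4 of 320 women. In Group 2 it is 0.3 × 0.85 × 0.20 × 0.5 = 2.55%, or 8.2 of 320.

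A more extreme set (f = 10%, c = 40% v 30%, v = 25% in both arms) gives 0.5 × 0.9 × 0.40 × 0.75 − 0.3 × 0.9 × 0.30 × 0.75 = 13.5% − 6.1% = 7.4 points. If v may differ freely between arms at those rates, with every such booking attended in one arm, the difference runs from −6.1 to +13.5 points. Nothing in the plan suggests that booking after a clean SSE would be that common.

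**Tests.** Comparing the section 1.0 hypothesis with sections 3.4 and 14.0, scheduling appears in no test. The nearest is having seen a dermatologist, in section 3.4 only.

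**The case against.** The strongest reply is that the study promotes booking mainly for women who find something. The one-week reminder in section 3.3 prompts an appointment only if a concerning mole is found, and the changing-room cards concern appointments for concerning lesions. On that view few clean-SSE women would book, follow-up in the hypothesis means follow-up of a lesion, and seeing a dermatologist is the harder and better outcome. Much of this stands: it is why the low rows of the table are plausible. It does not remove the mismatch, because section 3.1 itself describes the booking question without that condition.

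The telephone script might also carry an unconditional question. That could close the one-month gap. It would not change the printed REDCap items or the missing test.

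Some stronger readings do not hold:

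- A reader might infer a large loss of power. If booking without SSE is also set at 30% v 20% and 60% of mole finders book, row five gives a true difference of 10.45 points (32.25% v 21.80%) recorded as 6.63, and power falls from about 85% to 52% (320 per arm, two-sided 5%, no allowance for allocation by week). But no such test is planned, and the case assumes that clean-SSE women book as often as women who did no SSE. With 5% booking after a clean SSE in both arms, 3.65 points become 3.2.
- A reader might count the section 3.2 survey as another missed chance. That section places it as women leave the changing room, and section 12.0 calls the one-month survey the second, so it could not record later bookings.
- A reader might take appointment information as unique to Group 1. Section 3.1 also puts appointment cards in all eight changing rooms.
- A reader might conclude that Aim 2 is defective. Its two branches match the three-month items, so rewording it would be a preference.

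**Conclusion.** The point holds on the printed items. The hypothesis and section 3.1 call for appointments made, the surveys record them for only some women, and no test uses them. Sections 3.1 and 3.3 also disagree on whether Group 2 is surveyed at one month. If section 3.3 were followed, Group 2 would have no one-month data.

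The consequence is limited. The booking gap leaves the planned comparisons untouched, although the missing start date in item 9 bears on the comparison of having seen a dermatologist. The documents do not allow the size or direction of the gap to be derived. It is near zero if few clean-SSE women book or if all have attended by three months, and a few percentage points under less favourable assumed rates. Because it is cheap to close before data collection and cannot be closed afterwards, it should be corrected.

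**What to change.** - Add one question for every woman in both groups at one and three months: *Since your mammogram, have you made an appointment with a dermatologist about your skin?* Items 7 and 8 can stay.
- Tie item 9 to the period since the mammogram, and reword the EMR review paragraph so that a yes means a visit held.
- Correct section 3.3 so that the one-month survey goes to both groups, as section 3.1 says.
- Add appointment made by three months to section 3.4 as a secondary between-group comparison, reported as a difference with its 95% confidence interval.

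Aim 2 and the primary outcomes can stay as they are. The cost is one extra item per survey and one more test, labelled secondary because it adds to the number of comparisons. No participants are added, and no contacts beyond those section 3.1 already plans.

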3.3 Research procedures and activities

Follow-Up

1 week after the mammogram, RA will contact participants in group 1 via their preferred method to remind them to perform SSE and schedule a dermatologist appointment if they find a concerning mole. (see attached telephone script)

1 month after the mammogram, the RA will call participants in group 1 and administer a survey to see if they checked their skin and/or made an appointment with a dermatologist.

Effect of SSE education delivered during the mammography experience.

(see attached telephone script) An anonymous REDCap survey may be used in place of the telephone call, depending on participant's preferred method of contact preference.

The survey questions are as follows:

1. Did you read the brochure?
 Yes No
2. Did you check your skin? (If no, please proceed to question #4)
 Yes No
3. If yes, did you notice any concerning moles?
 Yes No
4. If no, will you consider checking your skin in the future?
 Yes No
5. If you found any concerning moles, did you make an appointment to see a dermatologist?
 Yes No

If no, do you intend to do so in the near future?

6. Did you share the brochure with anyone else?
 Yes No
7. If yes, who did you share it with:
 - a) A relative: son, daughter, father, mother, sister, brother
 - b) A friend : woman, man
 - c) Someone I work with: woman, man

REDCap Survey

3 months after the mammogram, an anonymous REDCap survey will be emailed to each woman enrolled in both groups. If participants do not complete the REDCap survey in 2 weeks, they will be called and surveyed via telephone. The following items with relevance to the research:

1. Do you have a history of sunburn? Yes/No
2. Do you have a history of more than 10 indoor tanning sessions? Yes/No
3. Do you have a personal or family history of melanoma? Yes/No
4. Have you ever performed a skin self-examination prior to your most recent mammogram? Yes/No

Effect of SSE education delivered during the mammography experience.

5. Did you perform a skin self-examination after your most recent mammogram?
Yes/No
If no, then go to item 8.
6. Did you find a concerning mole? Yes/No
7. If you found a concerning mole, did you make an appointment to see a dermatologist? Yes/No
8. If you did not perform a skin self-examination, did you still make a follow-up appointment to see a dermatologist for a skin examination? Yes/No
9. Have you had an appointment with a dermatologist yet? Yes/No

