14.0 Data Analysis

14.1. This convenience sample of women undergoing screening mammography will all receive education either as a brochure and a 1-week reminder or as only the brochure. Demographic characteristics of the two groups will be examined using means and standard deviations (age) and counts and percentages for all categorical variables. Primary outcomes of SSE performance, biopsy, and diagnoses will be compared using Chi-square tests of association or Fisher's exact tests where sample sizes were restrictive. Due to the skewed nature of the anxiety scale, a Wilcoxon rank sum test will be used to compare anxiety, the secondary outcome, in the two groups. Descriptive statistics will be performed for the tertiary outcome of dissemination.

15.0 Confidentiality and Data Management:

1. There are no biological specimens. All of the following data is collected in person consent and responses to structured interviews and focus groups.
2. Our systems are guarded against outside entry by Northwestern's own firewall supporting 128-bit encryption. This level of encryption provides the highest level of protection against hackers, computer break-ins, etc. All data is deidentified. Experienced research assistants will be employed and will receive training that includes emphasis upon the importance of confidentiality of information, and all personnel on the project will complete the required NIH training in the protection of human research participants.
3. Data will be retained in separate locked file cabinets and on computers with restricted and password protected access, without links to the master code list. All data based on the research will be reported in aggregate form. No individual respondents will be identified. Electronic data will be maintained in a study specific database on the server of the Department of Dermatology at the Feinberg School of Medicine. Paper-based files will be kept in a locked cabinet in a locked room within the Northwestern University Department of Dermatology research offices. Identifiable data will be kept separate from the case report forms and source documents. Data gathered as a result of this study are available to inspection on request by Food and Drug Administration or other government regulatory agency auditors, and the Northwestern University Institutional Review Board (IRB).

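### Aim 1 asks whether SSE education encourages SSE, but both arms are educated and the plan has no comparator or analysis for that question, so the trial can only describe it

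*Combined protocol and SAP*

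**What the plan says.** Section 1.0 sets two aims. Aim 1 is "Assess whether SSE education introduced during routine screening mammography encourages women to implement SSE at home", and it also names lesions found and dermatology follow-up. Aim 2 concerns what reminders and scheduling information add.

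Section 3.1 (Study Design) gives both groups the brochure. In addition, every changing room "will be equipped with a poster, brochures (Fig 1 and Fig 2) and cards with information about obtaining an appointment with a dermatologist". Group 1 is also handed a scheduling card and gets a reminder at one week. Section 14.0 confirms that the women "will all receive education either as a brochure and a 1-week reminder or as only the brochure".

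The survey items that bear on change are in Section 3.3 (Research procedures and activities), on the 3-month form. Item 4 asks "Have you ever performed a skin self-examination prior to your most recent mammogram", and item 5 asks "Did you perform a skin self-examination after your most recent mammogram". On timing: "3 months after the mammogram, an anonymous REDCap survey will be emailed to each woman enrolled in both groups". Women who have not completed it within 2 weeks are telephoned.

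Section 3.4 plans descriptive counts by group and a chi-square comparison of the groups on SSE and dermatology visits. Section 14.0 plans chi-square or Fisher's exact tests of SSE, biopsy and diagnoses. Neither section uses item 4, names an outside benchmark or sets a criterion for Aim 1.

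**The concern.** Whether education encourages a behaviour is a question about effect, and it needs some account of what the women would have done without the education. An arm comparison in which everyone is educated does not supply this. If the between-arm test is positive, it supports the reminder and card; if it is negative, it says nothing against the brochure and poster.

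What remains for Aim 1 is a percentage of women who did SSE after the visit. That figure includes women who would have examined their skin anyway, and the plan has no means of separating them. Section 11.0 expects the study to inform whether such education is worth wide use in mammogram facilities. A conclusion of that kind, drawn from the raw percentage, would be unsound.

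**Working it through.** The documents give no expected rates, power or effect size for Aim 1, so there is no plan figure to reproduce. The check sets each part of the aim against the data and analyses available.

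**1. What the arm contrast isolates**
- Shared by both arms: poster, brochures and cards in the changing rooms; brochure given to each woman.
- Group 1 only: scheduling card handed over, and a one-week reminder.
- The contrast therefore estimates the added components, which is Aim 2.

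**2. What pre-visit information exists**

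| Part of Aim 1 | Pre-visit item | Post-visit item |
|---|---|---|
| SSE | Item 4, lifetime | Item 5, about 3 months (longer for late responders) |
| Concerning lesion found | None | Item 6 |
| Dermatology follow-up | None | Items 7 to 9 |

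The survey in Section 3.2 and the 1-month survey in Section 3.3 also ask whether the woman checked her skin, but neither refers to a period before the visit.

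**3. What the trial can estimate**
- Completers: 800 × (1 − 0.20) = 640, or 320 per arm.
- Largest 95% half-width for post-education SSE, all women: 1.96 × √(0.25/640) = 0.039, or 3.9 points.
- One arm: 1.96 × √(0.25/320) = 0.055, or 5.5 points.
- First-ever SSE among women answering No to item 4. If 30% to 70% have never done SSE (assumed), there are 640 × 0.30 = 192 to 640 × 0.70 = 448 such women. The largest half-widths are 1.96 × √(0.25/192) = 7.1 points and 1.96 × √(0.25/448) = 4.6 points.

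These are adequate descriptions of uptake, but this precision does not bear on whether education caused the uptake.

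**4. Why item 4 cannot serve as the before value for item 5**

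This is illustrative only: the rates are assumed, and the plan does not propose the comparison. Suppose education has no effect, a share *h* of women do SSE at a constant rate of *λ* per year, and *ever* means the last 10 years. Then:
- Ever before = *h*(1 − e^(−10λ))
- Within 3 months after = *h*(1 − e^(−λ/4))

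| *h* | *λ* | Ever before | 3 months after | Difference |
|---|---|---|---|---|
| 30% | 4 | 30.0% | 19.0% | −11.0 points |
| 50% | 2 | 50.0% | 19.7% | −30.3 points |
| 70% | 0.5 | 69.5% | 8.2% | −61.3 points |

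Over *h* from 30% to 70% and *λ* from 0.5 to 4, the apparent fall runs from 11 to 61 points with no true change. The size depends on the assumptions. The direction does not: if SSE frequency is stable, a longer look-back gives a proportion at least as high.

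**The case against.** The strongest reply is that Aim 1 was always descriptive. Section 1.0 introduces the study as an evaluation of SSE among women who receive information at the mammogram, its only hypothesis is the between-arm one, and the counts in Section 3.4 fit that reading. This largely stands, and the fix adopts it. However, the aim's verb and the running title both speak of an effect, so the wording has to change to match.

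A reader might infer three stronger things that the documents do not support.

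- *That the trial would report a fall in SSE.* No section plans to subtract item 4 from item 5. The mismatch matters only if someone later tries to fill the gap with those items.
- *That items 4 and 5 are useless together.* They are on the same form, so they pair within a woman. No on item 4 with Yes on item 5 identifies first-ever SSE, and for that measure a lifetime look-back is the right one.
- *That no other evidence exists.* The surveys ask whether the woman noticed the information, thought it applied to her and read the brochure. The arms can also be seen as two intensities of education. Both bear indirectly on Aim 1. But readers and non-readers are self-selected, and the two-intensity contrast shows what more contact adds, not what education does compared with none. Neither is planned as an analysis of Aim 1.

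It can also be objected that a baseline question needs linkage to a survey described as anonymous. Yet calls to non-responders, the EMR check triggered by item 9, and the subject numbers in Section 15.0 already require responses to be identifiable.

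**Conclusion.** The point holds as a mismatch between Aim 1 and the design. Both arms are educated, the planned tests answer Aim 2, the one pre-visit item uses a different window from its post-visit partner, and two of the three parts of Aim 1 have no pre-visit item. The trial can report post-education uptake to within about 3.9 points (given the plan's 20% attrition) and first-ever SSE among previous non-performers. It cannot attribute either to the education.

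This rests on the design and survey items alone. The 11 to 61 point range depends on assumed rates and is not an error the plan would produce. Aim 2 and the between-arm comparison are unaffected by this point. The change should be made because it is cheap and, without it, a conclusion on the first aim would be unsound.

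**What to change.** 1. Restate Aim 1 without a causal claim, for example: *describe SSE, concerning lesions found and dermatology follow-up after education, and the change in SSE from before the visit.*
2. Keep item 4, which identifies first-ever SSE. Add a matched question, *In the 3 months before this mammogram, did you check your skin?*, and a similar one for dermatology visits. On the 3-month form the SSE question pairs directly with item 5. It can go at enrolment instead if responses are linked by subject number.
3. Add to Section 14.0 the paired before/after difference in proportions with its 95% CI and a McNemar test, overall and by arm, plus first-ever SSE among women answering No to item 4. Lesions found remain a post-visit description.

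The cost is one or two survey questions, one paired analysis and one sentence of the aim. Three limits remain. On the 3-month form the pre-visit answer relies on recall. At either time point it is given after the woman has seen the poster and brochure, because Section 3.2 places consent after she leaves the changing room. And a before/after change is uncontrolled, so the claim is more modest than the current aim implies.
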